13.3 MONTH 6 PROCEDURES**13.3.1 Vital Signs**

Measure the participant's blood pressure and pulse using the Dinamap Monitor Pro 100 according to the instructions in Chapter 14.2. Enter the results on the VITAL SIGNS data form.

13.3.2 Weight and Abdominal Circumference

Ask the participant to remove her shoes and anything in her pockets. Weigh

her twice in kilograms on the Tanita BWB 800 digital scales, following the detailed directions in Chapter 14.1.4 (Physical Measurements). Calculate the average of the two measurements and record all results on the WEIGHT/ABDOMINAL CIRCUMFERENCE data form.

Ask the participant to lift her blouse and measure the circumference of her waist with the Gulick tape according to the detailed procedures in Chapter 14.1.5. Remove the tape and then make a second measurement. Record all results on the WEIGHT/ABDOMINAL CIRCUMFERENCE data form. Calculate the difference between the measurements using the calculator. If the difference between Measurement 1 and Measurement 2 is equal to or greater than 1 cm make a third measurement and record it on the data form.

13.3.3 Concurrent Medications and Serious Adverse Events

Ask the participant if she has seen her doctor, been hospitalized or experienced any serious health events in the past six months. Any events that meet the definition of “Serious Adverse Event” (SAE), described in Chapter 17 of the PRIDE Operations Manual, must be reported to your IRB and documented on the SAE Form. Please note that SAEs should be reported as soon as you are made aware of them. This follow-up visit provides an additional occasion to check for events that may have happened to participants you haven’t seen frequently. The responses to questions 1 and 2 on the Cost Analysis form may be a cue to probe further for SAEs as well, however, these questions relate only to the past three months. Please review all self-administered questionnaires before the participant leaves the site. If you are uncertain whether a medical visit or health event qualifies as an SAE, please contact the Coordinating Center for advice.

Ask the participant if she has had any changes in prescription medications, or started or stopped medications. Check to see if she has started or stopped over-the-counter medications also. The participant should bring to the visit all prescription and non-prescription medications that she takes on a regular basis. Look at each medication and record either the trade name (preferably) or the generic name of each medication, but not both. Record over-the-counter medications only if they are taken on a regular basis.

Please record all medications even if there has been no change since baseline.

If the participant is not taking any medications regularly, print “NONE” in the

boxes after “1. Trade Name.”

13.3.4 Questionnaires

Most questionnaires have been administered previously during screening or randomization visits and instructions for each can be found in Chapter 10 or Chapter 12. The Beck Depression Inventory must be completed and reviewed on-site. It might be helpful to complete the Paffenbarger on-site so that staff can assist the participant. As during screening, the Sexual Function questionnaire should be accompanied by a stamped, addressed envelope, completed off-site and sent directly to the Coordinating Center. Whether other questionnaires are completed on- or off-site is left to the discretion of study staff. All questionnaires to be completed off-site should be mailed to the participant in advance so that she can complete them at home and bring them with her to the clinic visit. Please check the list at the beginning of Section 13.2 to be sure you have administered all questionnaires.

The following questionnaires are administered for the first time at this visit.

13.3.4.1 Participant Satisfaction Questionnaire

This one page form is designed to assess in general terms the participant’s perception of changes in her incontinence. Note that the questions ask her, at each of the follow-up visits, to compare her current experience with her pre-PRIDE experience.

13.3.4.2 Pelvic Muscle Questionnaire

The two page Pelvic Muscle Questionnaire is designed to elicit information about the extent to which all participants practice the exercises that are described in the “Staying Dry” handbook. If the response to question 1 is “Didn’t receive the booklet” the participant should not answer any of the other questions. If she forgot she had the booklet, lost it right away or claims she never received one she should mark this first response. PLEASE GIVE THE PARTICIPANT A BOOKLET AT THIS TIME if she doesn’t have one.

If the response is “Haven’t read the booklet” the participant should complete the questionnaire. It is possible that she may have received instructions about the pelvic muscle exercises from a different source

and may be practicing them anyway. Primarily, we want to know whether she is doing pelvic muscle exercises, regardless of the source of her information.

13.3.4.3 Cost Analysis (Follow-up)

The Cost-Analysis (Follow-up) questionnaire is an expanded 8 page version of the baseline questionnaire. Please be sure you have printed the correct version. Ensure that all questions are answered and the skip patterns are followed. If the response to question 1a, 1c or 1d is greater than 0 be sure to ascertain whether or not the participant has had a serious adverse event.

13.3.4.4 Motivation Questionnaire (Follow-up)

The Motivation Questionnaire (Follow-up) has several questions that are different from baseline. Please be sure you have printed the correct version. Ensure that all questions are answered according to instructions and that skip patterns are followed.

13.4 7-DAY VOIDING DIARY AND 24-HOUR PAD TEST

Review the instructions for the 7-day Voiding Diary and the 24 hour Pad Test carefully with each participant during the visit, according to the description in Chapters 9.3.3 and 10.4.2.8 of the Operations Manual (OM). If the participant claims to remember the instructions, praise her for doing so but probe a little further for detail, for example: "Are you clear about the difference between an urge episode and a stress episode of incontinence? That can be pretty confusing at times." Give her the printed instructions for each test to take home. Give the participant the long or short form of the 7-day Voiding Diary, depending on the number entries she made during the screening phase. Offer her the new compact size diary only if the size of the original diary was a problem for her in the past, and only if she uses the short form of the diary. (The compact version does not have as many pages as the long version of the diary.)

Provide a self-addressed, pre-paid UPS mailer that will hold both the Pad Test kit and the diary. Ask the participant to complete the diary and the pad test in the week following her visit, and to mail the pads and diary back to you as soon as they have been completed. If it is inconvenient for the participant to complete the diary and pad test the next week, determine when she will start the diary and schedule a reminder call to her the day before. Optimally, the pad test should be completed for a 24-hour

period during the same week that the 7-day voiding diary is completed.

When the diary and pads are returned, review both for accuracy and completeness. The diary review should be done according to the instructions in Chapter 10.3.2.2 of the OM. Complete the Voiding Diary Data Entry form according to the instructions in Chapter 10.3.2.3. During follow-up, failure to complete the diary properly does not disqualify the participant from PRIDE. However, this is the primary outcome data and every effort should be made to ensure that the diary is completed properly for at least five out of seven days. If this requirement is not met, offer to mail another diary immediately and ask the participant to try to fill the diary out again. Discuss any issues that may have impacted her ability to follow the instructions.

Weigh the pads as soon as you receive them and fill out the rest of the Pad Test form according to the instructions in Chapter 10.4.2.8.7 of the OM. If the participant has forgotten to fill out the labels on the bags containing the pads please call her to obtain the correct information.

When all procedures and forms, including the 6 month checklist, have been completed, fax them to the data system at the Coordinating Center.

13.5 RANDOMIZATION TO WEIGHT MAINTENANCE PROGRAMS

The weight loss intervention groups will be assigned randomly to either a motivation-based or a skills-based motivation program. The random assignment will be made just before the final session of the weight loss intervention program. The study coordinator or interventionist will contact the project assistant at the Coordinating Center to receive, by e-mail, the maintenance phase assignment for each intervention group. Study center staff will send an email back to the Coordinating Center confirming assignment of the maintenance groups. Participants will not be informed of the group assignments.

13.6 MONTH 12 VISIT

13.6.1 Preparation for the Visit

If an appointment was not scheduled at the previous visit, the participant should be contacted at least one month prior to the target date to schedule the follow-up visit. Reminder calls, letters or postcards can be sent to help avoid no-shows and to provide some information about the visit.

Let the participant know that this visit is different from the classes or sessions in which she has been participating and let her know the approximate length of the visit. Ask her to bring with her all the prescription and non-prescription medications that she takes regularly. In order to maintain the blind, remind the participant that she should not discuss her group assignment with any of the staff during the clinic visit.

Several of the self-administered questionnaires may be mailed ahead of time so that the participant can complete them at home and bring them with her to the visit. The Beck Depression Inventory should not be mailed, but should be completed and reviewed during the visit.

Forms/Supplies Needed for Month 12 Visit

- 12-Month Checklist
- Weight and Abdominal Circumference
- Vital Signs
- Concurrent Medications
- Serious Adverse Event Form (if needed)
- Food Frequency Questionnaire
- Incontinence Impact Questionnaire (IIQ)
- UI Symptoms
- Urogenital Distress Inventory (UDI)
- Paffenbarger Activity Questionnaire
- Short form – 36
- Sleep Questionnaire
- Sexual Function Questionnaire
- Bowel Habits
- Beck Depression Inventory (complete in clinic)
- Participant Satisfaction Questionnaire
- Pelvic Muscle Questionnaire
- Health Utilities Index
- Cost Analysis (Follow-up)
- Motivation Questionnaire (Follow-up)
- 7-Day Voiding Diary
- 24-Hour Pad Test Kit
- Month 12 Participant Thank You gift – gym bag

Please have a calculator available.

13.6.2 Vital Signs

Measure the participant's blood pressure and pulse using the Dinamap Monitor Pro 100 according to the instructions in Chapter 14.2. Enter the results on the VITAL SIGNS data form, marking the Month 12 bubble.

13.6.3 Weight and Abdominal Circumference

Ask the participant to remove her shoes and anything in her pockets. Weigh her twice in kilograms on the Tanita BWB 800 digital scales, following the detailed directions in Chapter 14.1.4 (Physical Measurements). Calculate the average of the two measurements and record all results on the WEIGHT/ABDOMINAL CIRCUMFERENCE data form, marking the month 12 bubble.

Ask the participant to lift her blouse and measure the circumference of her waist with the Gulick tape according to the detailed procedures in Chapter 14.1.5. Remove the tape and then make a second measurement. Record all results on the WEIGHT/ABDOMINAL CIRCUMFERENCE data form. Calculate the difference between the measurements using the calculator. If the difference between Measurement 1 and Measurement 2 is equal to or greater than 1 cm make a third measurement and record it on the data form.

13.6.4 Concurrent Medications and Serious Adverse Events

Ask the participant if she has seen her doctor, been hospitalized or experienced any serious health events in the past six months. Any events that meet the definition of "Serious Adverse Event" (SAE), described in Chapter 17 of the PRIDE Operations Manual, must be reported to your IRB and documented on the SAE Form. Please note that SAEs should be reported as soon as you are made aware of them. This follow-up visit provides an additional occasion to check for events that may have happened to participants you haven't seen frequently. The responses to questions 1 and 2 on the Cost Analysis form may be a cue to probe further for SAEs as well, however, these questions relate only to the past three months. Please review all self-administered questionnaires before the participant leaves the site. If you are uncertain whether a medical visit or health event qualifies as an SAE, please contact the Coordinating Center for advice.

Ask the participant if she has had any changes in prescription medications, or

started or stopped medications. Check to see if she has started or stopped over-the-counter medications also. The participant should bring to the visit all prescription and non-prescription medications that she takes on a regular basis. Look at each medication and record either the trade name (preferably) or the generic name of each medication, but not both. Record over-the-counter medications only if they are taken on a regular basis.

Please record all medications even if there has been no change since the previous visit.

If the participant is not taking any medications regularly, print "NONE" in the boxes after "1. Trade Name."

13.6.5 Questionnaires

All questionnaires were administered previously at the Month 6 visit and instructions for each can be found in Chapters 10, 12 or Chapter 13.3.4 . The Beck Depression Inventory must be completed and reviewed on-site. It might be helpful to complete the Paffenbarger on-site so that staff can assist the participant. As before, the Sexual Function questionnaire should be accompanied by a stamped, addressed envelope, completed off-site and sent directly to the Coordinating Center. Whether other questionnaires are completed on- or off-site is left to the discretion of study staff. All questionnaires to be completed off-site should be mailed to the participant in advance so that she can complete them at home and bring them with her to the clinic visit. Please check the list at the beginning of Section 13.6 to be sure you have administered all questionnaires.

13.7 MONTH 18 VISIT

Forms and procedures for the Month 18 visit are the same as those described for Month 12 (Chapter 13.6) with the addition of the Exit Questionnaire. As always, please make every effort to obtain physical measurements, voiding diaries and pad tests for all participants in addition to the questionnaires.

At the end of the visit be prepared to inform the participant about the group end-of-study celebration at which time she will hear more about incontinence. Be prepared to inform the participant about when and how she will receive results of the study when all participants are finished and the data analysis is completed. Update contact information if necessary.

Thank the participant for the contribution she has made and present her with the end of study gift.

13.7.1 Exit Questionnaire

Three Exit Questionnaires have been developed to assess the participant's opinion of the PRIDE Structured Education Program, Skills-based Maintenance Program, and Motivation-based Maintenance Program. The Structured Education Exit Questionnaire has one question, while the Skills-based Maintenance Program and Motivation-based Maintenance Program Questionnaires have several questions divided into Section I (maintenance in general) and Section II (program specific content). For each participant, please be sure you have printed the correct version. Ensure that all questions are answered according to instructions.

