8.4.12. Other Measurements. Variables that may act as predictors or moderators of the efficacy of weight reduction for reducing the frequency of incontinence will be documented at baseline. These covariates include demographic characteristics (age, race/ethnicity, relationship status, education, annual family income), general health, genitourinary history (duration of incontinence, prior type and duration of therapy, amount of urine loss, pad use, drinking habits), reproductive health (gravity, parity, route of delivery, menopause status, hormone therapy use), medical history (hypertension,

pulmonary disease, stroke, diabetes, surgical history (hysterectomy, pelvic organ prolapse repair, other pelvic or abdominal surgery), and medications.

8.4.13. Ensuring Objective Assessments. Throughout the study every effort will be made to ensure objective and blinded assessments of outcomes. Although participants will be told the name of their treatment assignment they will not be provided details about the intervention techniques of the other treatment groups. Focus will instead be maintained on the support group to which they are assigned.

Staff who review the voiding diaries and record participant weight at the 6, 12 and 18 month assessments will not be informed of the participant's treatment assignment and will not participate in the delivery of the study interventions. Likewise, staff who perform the urodynamic studies will not be informed as to the participant's treatment assignment. Care will be taken to avoid overtly identifying treatment assignments on participant charts.

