Appendix 14A: Stadiometer Calibration Log

Appendix 14B: Scale Calibration Log

14.0 PHYSICAL MEASUREMENTS

14.1 HEIGHT, WEIGHT AND ABDOMINAL CIRCUMFERENCE

14.1.1 Overview of Body Size Measurements

Equipment used for body size measurements in PRIDE will be the same equipment used in the Look AHEAD study. Procedures are similar also but the measurement units may be different in PRIDE and the instructions should be reviewed carefully before measurements begin.

Change in body weight is a primary measure of effectiveness of the interventions in this trial. Body weight relative to height, expressed as Quetlet's index, or body mass index (BMI, kg/m^2), is an index of fatness highly correlated with more direct measures of body fat. Abdominal (waist) circumference and changes in waist circumference are indicators of subcutaneous and visceral fat deposits in the abdominal region.

Participants should wear light clothing, e.g., a short sleeve shirt or blouse (or surgical gown), shorts, socks but remove shoes (for weight and height) and items in pockets. A supply of gowns should be maintained at the clinic for participants who forget to wear or bring the appropriate clothes for body size measurements.

Staff who are masked to the intervention assignment of the participant should make body size measurements. If possible, a team of two people, one acting as observer and the other as recorder, should perform the measurements. The observer takes the measurements, reporting the results to the recorder, who repeats them. The observer keeps the measuring instrument in place until the recorder repeats the number. The recorder generally checks the participant's position during the procedure. If a second observer is not available, a mirror can be used to check for the correct position (e.g., whether the tape is horizontal for waist circumferences). Have a calculator available for the required calculations or complete the calculations after the visit is over and before faxing the form to the Coordinating Center.

Height and weight will be measured during screening and BMI will be calculated to determine eligibility. Weight and abdominal circumference will be measured at the randomization visit and at months 6, 12 and 18. Weight only will be measured at month 3.

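### The Month 18 Exit Questionnaire reveals each woman's arm to whoever handles it, and Chapter 13 does not keep it away from the staff who must stay masked

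*Protocol*

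**What the plan says.** Three places protect the blind at follow-up.

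- Protocol 8.4.13 concerns "Staff who review the voiding diaries and record participant weight at the 6, 12 and 18 month assessments". They are not to be told the treatment assignment and take no part in delivering the interventions.
- Manual 14.1.1: "Staff who are masked to the intervention assignment of the participant should make body size measurements".
- Manual 13.6.1, on the Month 12 visit, gives keeping the blind as its reason and tells staff to "remind the participant that she should not discuss her group assignment with any of the staff during the clinic visit".

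Section 13.7 carries that visit forward: "Forms and procedures for the Month 18 visit are the same as those described for Month 12", with the Exit Questionnaire added. Section 13.7.1 then describes the form: "Three Exit Questionnaires have been developed to assess the participant's opinion of the PRIDE Structured Education Program, Skills-based Maintenance Program, and Motivation-based Maintenance Program". The control version has a single question. The two maintenance versions have several, and their second section is specific to the programme. The instruction is "For each participant, please be sure you have printed the correct version", followed by a request to see that every question has been answered.

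**The concern.** The version of the form is the arm. Nobody can select it, hand it out or check it for completeness without learning whether the woman is in Structured Education, skill-based or motivation-based maintenance. Asking her not to mention her group achieves little if the paperwork discloses it.

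Month 18 supplies the closing weight for Aim 2 (primary) and the closing diary for Aim 4 (secondary). If the person who reviews the diary has handled the form, knowledge of the arm can affect how far missing entries are pursued and how unclear ones are settled. Masking lost in this way cannot be restored in the analysis.

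**Working it through.** No power or sample size figure bears on this point, so the check sets the instructions side by side.

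**1. Does handling the form reveal the arm?** Yes. There are three versions for three programmes (13.7.1). The control form can be told from the others by its length alone.

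**2. Does Chapter 13 keep the form away from assessors?** No. The same unnamed reader is told to
- weigh the woman twice (13.6.3, carried to Month 18 by 13.7),
- review all self-administered questionnaires before she leaves (13.6.4),
- review the diary when it is returned (13.4), and
- print the right Exit Questionnaire and see that it is complete (13.7.1).

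No role is split off, no sealed return is given, and nothing says that the form must wait until weight and diary are final.

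**3. Could the form be handled before the outcomes are settled?**
- *Weight.* Possibly. The form is printed for the visit, and 13.6.5 has questionnaires that are completed off site mailed out beforehand.
- *Diary.* Probably. Sections 13.1 and 13.4 have the diary given out at the visit, mailed back and reviewed on return, so after the visit forms have been dealt with. Protocol 8.3.5 instead has the diary mailed ahead and brought to the visit. Even then nothing puts its review before the Exit Questionnaire.

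**4. How much room for judgement does each outcome leave?**
- *Weight (Aim 2).* It is read to 0.1 kg on a digital display, twice, and averaged (14.1.4, 13.6.3). There is little room.
- *Diary (Aim 4).* Section 13.4 sends the reviewer to 10.3.2.2, which asks staff to probe for missing data. One worked example is an entry where the woman did not say whether she leaked. Settling that entry changes the weekly count. Deciding between urge, stress and other changes the type but not the total. The repeat summary at the Coordinating Center (8.4.1) works from the reviewed diary, so it would not detect an entry completed under prompting. Section 10.3.2.2 also says that diaries are sent there only on request.
- *Quality of life (Aim 5).* The IIQ, UDI and SF-36 are filled in by the woman, and 8.4.13 does not set masking for them.

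**5. How many women?** Section 9.5 expects 85% of 330 at 18 months: 0.85 × 330 = 280.5, given there as 280. This is an upper bound, reached only if an assessor handles the form for every attendee.

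**6. Was a safeguard at hand?** Yes. The Sexual Function Questionnaire goes to the Coordinating Center in an opaque envelope (10.4.2.6) and does so again at follow-up (13.6.5). The Exit Questionnaire was not given this route.

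**The case against.** The best reply is that the passages can all be obeyed at once. Section 13.7.1 does not say that the weigher or the diary reviewer prints the form. The reader whom Chapter 13 addresses must be the whole site: 13.5 sends maintenance assignments to the coordinator or interventionist, and 13.8 suggests calls to women in the education group, so some of these tasks already need unmasked staff. Section 8.4.13 states the separation of roles and can be read as governing. Even the lowest website access level, meant for intervention staff, covers everything except participant data (18.3.1), and the forms can be downloaded there (18.4), so an interventionist could print the form. The protocol also admits that the interventions are not strictly blinded (8.2.1).

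Much of this stands. It rules out the stronger readings that a reader might infer: that the people who weigh each woman and review her diary are necessarily unmasked, that the Aim 2 endpoint is compromised, that Aim 5 is affected, or that masked assessment at 18 months can no longer be claimed. The documents show none of these. Face-to-face probing is also not the default for a diary that is mailed back, although 10.3.2.2 still governs its review and a later contact remains possible.

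The reply does not remove the gap. A compliant arrangement is possible but nowhere required. A site that followed Chapter 13 literally, including the instruction to review all self-administered questionnaires before the woman leaves, could have an assessor learn the arm without breaking any instruction in that chapter.

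**Conclusion.** The point holds as a risk to masking that the manual itself creates. At Month 18 the instructions put knowledge of the arm into the hands of visit staff, and no barrier is written between them and the assessors whom 8.4.13 and 14.1.1 require to be masked.

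The main exposure is the 18-month diary, and so secondary Aim 4. For weight, and so primary Aim 2, the risk is small. Aim 5 is not touched through assessor masking. Up to about 280 women are concerned. The size of any bias cannot be calculated from the documents, because they do not say who handles the form or how often diary entries need completing on review.

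The conclusion assumes that visit staff at a site may share tasks, which Chapter 13 allows. Where a site already uses a separate unmasked person for the form, the problem does not arise there.

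**What to change.** Amend 13.7.1 to say that staff who record weight or waist, or who review diaries, do not print, hand out or check the Exit Questionnaire. Then use one of two routes:

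- an interventionist or coordinator who already knows the assignment and has no assessment role handles the form; or
- the form goes out in a sealed envelope and is returned directly to the Coordinating Center, as for the Sexual Function Questionnaire.

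The general instruction in 13.6.4 to review all self-administered questionnaires should exempt this form, so that the two sections agree. The form asks for the woman's opinion of her programme, so the sealed route has the further merit that the person who led her group does not read her answers.

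The cost is a few sentences in Chapter 13, minor handling or postage, and possibly a few lost or incomplete forms. No outcome analysed under Aims 1 to 5 depends on them. The change should be in place before Month 18 visits take place.
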